5 STUDY ASSESSMENTS AND PROCEDURES

5.1 Pre-Treatment Period

During the Pre-Treatment Period, subjects are consented and qualified (screened) for the study. Informed consent must be obtained before initiation of any clinical screening procedure that is performed solely for the purpose of determining eligibility for this study. Evaluations performed as part of routine care before informed consent can be considered as screening evaluations if done within the defined screening period, and if permitted by the site's institutional review board (IRB)/ethics committee (EC) policies.

Study eligibility is based on meeting all of the study inclusion criteria and none of the exclusion criteria at screening and on Study Day 1 before study treatment administration. The following assessments will be conducted before subjects receive their first dose of cabozantinib on this protocol:

- 1. For patients with measurable visceral metastases CT scans with contrast or MRI are required. Bone scan is required for patients with visceral metastases who also have bone metastases.
- For patients with only bone metastases FDG-PET/CT scan is the only radiographic test required. FDG-PET/CT assessment will include standard assessment of SUV_{max}, as well as advanced volumetric measures including SUV_{peak}, metabolic tumor volume (MTV), and total lesion glycolysis (TLG)
- 3. Laboratory testing (chemistry, hematology tests, interleukin-6, c-reactive protein, thyroid function tests, urine analysis, and thyroid function tests)
- 4. EKGs will be performed at baseline.
- 5. Plasma metanephrines and chromogranin A will be obtained at baseline.

- 6. Evaluation of cancer symptoms by the MD Anderson Symptom Inventory (MDASI) will be obtained at baseline
- Physical examination, safety and adverse events evaluation will be performed at baseline.

For each subject, the Pre-Treatment Period ends upon receipt of the first dose of study treatment or final determination that the subject is ineligible for the study.

5.2 Treatment Period

During the Treatment Period, subjects will receive cabozantinib until either disease progression (unless the investigator, with approval of the Medical Monitor, judges the patient is deriving clinical benefit), the occurrence of unacceptable drug-related toxicity or for other reason(s) for subject withdrawal as described in Section 2.5. Subjects should be instructed to immediately inform the principal investigator (PI) of any AEs. Subjects experiencing dizziness, sleepiness, or other symptoms that could influence alertness or coordination should be advised not to drive or operate other heavy machinery.

The following schedule of assessments applies to all subjects (Table 5-1). More frequent assessments should be obtained if clinically indicated.

Table 5-1: Study Assessments

		Post-Treatment Period		
	Within 28 days before 1st Dose of Study Treatment	Within 4 days before the first dose of Study Treatment	Day 1 of Weeks 3, 5, 7, 9, then every 4 weeks through Week 24, then every 8 weeks (± 5 days); after week 52, every 12 weeks (+/- 5 days)	30 - 37 Days after last dose
Informed consent	X			
Demographics	X			
Medical and cancer history/demographics	X			
Physical examination	X	X	X	X
Height	X			
Weight	X	X	X	X
Vital signs	X	X	X	X
ECOG performance status	X	X	X	X
Clinical laboratory tests ¹	X	X	X	X
Urinalysis and UPCR	X	X	X	X
PT/INR, PTT	X	X	X^2	
TFTs (TSH, free T3, free T4)	X	X	X^2	
12-lead ECG	X	X	X^2	X
Cabozantinib administration			X (daily)	
Pregnancy test	X	X	X^2	X
Tumor assessment ³	X		X^3	
Bone scan ⁴	X		X^3	
FDG-PET CT ⁵	X		X^3	
Plasma Metanephrines and Chromogranin A ⁶	X		X^3	
Interleukin-6 and c- reactive protein, CTx	X		X ³	
Concomitant medications	X	X	X	X
MDASI ⁸	X	X	X (weekly)	X
Adverse events	Continuous			X
Follow-up				X
Nurse phone call ⁷			X (starting after week 24) ⁷	

ECG, electrocardiogram; ECOG, Eastern Cooperative Oncology Group; PT/INR, prothrombin time/International Normalized Ratio; PTT, partial prothrombin time, TFT, thyroid function test; UPCR, urine protein/urine creatinine ratio ¹Laboratory tests should include a standard hematology panel (CBC, differential, platelets) and chemistry panel (albumin, alkaline phosphatase, ALT, amylase, AST, bicarbonate, bilirubin, blood urea nitrogen, calcium, chloride, creatinine, glucose, lactate dehydrogenase, lipase, magnesium, phosphorus, potassium, sodium, total bilirubin, total

protein). CTx will be done, if patient has bone metastases, at screening and every 8 weeks during the first 52 weeks, then every 12 weeks.

If the subject is unable to have a study assessment taken within the defined time window due to an event outside of his or her control (eg, clinic closure, personal emergency, inclement weather, vacation), the assessment should be performed as close as possible to the required schedule.

Regular tumor assessments should be performed in accordance to the guidelines in Section 5.5 to determine if PD is present.

The Treatment Period ends when a subject receives his or her last dose of study treatment; the subject then enters the Post-Treatment Period.

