A recently published retrospective intention-to-treat study described potential clinical benefits derived from sunitinib in patients with metastatic PHs and PGs⁷. Seventeen patients with progressive disease over a period of 6 months were treated with 37.5-50 mg of sunitinib daily, 4 weeks on, 2 weeks off. Patients were followed with radiographic and biochemical studies every 2 to 3 months. As per RECIST 1.1, 8 patients (47%) exhibited clinical benefits: 3 patients had partial responses and 5 had prolonged stabilization of disease, including 4 patients with extensive skeletal metastases (but not other metastases) identified by18F-FDG-PET/CT scan. The tumors that responded to treatment also exhibited more than 30% reduction in glucose uptake 2-3 months after initiation of treatment compared with baseline. Patients who experienced partial response or prolonged stabilization of disease improved blood pressure and some discontinued treatment with antihypertensive medications. Most patients who benefited from sunitinib carried SDHB mutations. Unfortunately, most patients who experienced clinical benefits, later developed tumor progression⁷.

Hypothesis

Development of tumor progression and resistance to sunitinib may be related to the compensatory activation of molecular pathways that are not inhibited by this drug, such as the c-MET receptor pathway. MET and VEGFRs cooperate to promote tumor angiogenesis and MET upregulation may occur as a response to the VEGFs pathway inhibition leading to tumor resistance and growth8. MET activation is a common feature of human tumors and it is frequently observed in patients with bone metastases⁸. Molecular analyses of malignant PHs and PGs from a few patients participant of phase one clinical trials have found c-MET receptor gene mutations (unpublished data). Cabozantinib is a tyrosine kinase inhibitor with antiangiogenic and antitumor activity that targets the VEGF, c-MET, and RET receptors. This drug has been recently approved for the treatment of progressive metastatic medullary thyroid carcinoma another neuroendocrine tumor⁹. Of interest, cabozantinib has also shown effectiveness in patients with castration resistant prostate, breast, and renal cell carcinomas metastatic to the skeleton^{10, 11, 12}. Therefore, simultaneous inhibition of MET and VEGFRs by cabozantinib may provide a broad spectrum of antineoplastic activity and prevent tumor resistance in patients with malignant PHs and PGs.

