4.2 Exclusion Criteria

A subject who meets any of the following criteria is ineligible for the study:

- 1. Received cytotoxic chemotherapy (including investigational cytotoxic chemotherapy) or biologic agents (eg, cytokines or antibodies) within 3 weeks, or nitrosoureas/ mitomycin C within 6 weeks before the first dose of study treatment.
- 2. Prior treatment with cabozantinib
- 3. Radiation therapy for bone metastasis within 2 weeks, any other external radiation therapy within 4 weeks before the first dose of study treatment. Subjects with clinically relevant ongoing complications from prior radiation therapy are not eligible;
- 4. Received radionuclide treatment (i.e. I ¹³¹ meta-iodo- benzyl guanidine) within 6 months of the first dose of study treatment
- 5. Receipt of any type of small molecule kinase inhibitor (including investigational kinase inhibitor) within 14 days before the first dose of study treatment.
- 6. Receipt of any other type of investigational agent within 28 days before the first dose of study treatment.
- 7. The subject has not recovered to baseline or CTCAE ≤ Grade 1 from toxicity due to all prior therapies except alopecia and other non-clinically significant AEs.
- 8. Prothrombin time (PT)/ International Normalized Ratio (INR) or partial thromboplastin time (PTT) test ≥ 1.3 × the laboratory ULN within 7 days before the first dose of study treatment.
- 9. The subject requires concomitant treatment, in therapeutic doses, with anticoagulants such as warfarin or warfarin-related agents, heparin, thrombin or Factor Xa inhibitors, or antiplatelet agents (eg, clopidogrel). Low dose aspirin (≤ 81 mg/day), low-dose warfarin (≤ 1 mg/day), and prophylactic low molecular weight heparin (LMWH) are permitted.
- 10. The subject requires chronic concomitant treatment of strong CYP3A4 inducers (eg, dexamethasone, phenytoin, carbamazepine, rifampin, rifabutin, rifapentin, phenobarbital, and St. John's Wort).
- 11. The subject has experienced any of the following:
 - a. clinically-significant gastrointestinal bleeding within 6 months before the first dose of study treatment

- b. hemoptysis of ≥ 0.5 teaspoon (2.5ml) of red blood within 3 months before the first dose of study treatment
- c. any other signs indicative of pulmonary hemorrhage within 3 months before the first dose of study treatment
- 12. Radiographic evidence of cavitating pulmonary lesion(s)
- 13. Tumor invading or encasing any major blood vessels

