5.3 Post-Treatment Period

Subjects will return to the study site 30 to 37 days after their last dose of cabozantinib to complete end-of-study assessments.

Laboratory and physical examinations will be performed. Remaining study treatment will be returned by the subject, and treatment compliance will be documented. Additional follow-up will occur for subjects with AEs related to study treatment that are ongoing at the time of this visit, and for subjects with SAEs related to study treatment that occur after the time of this visit.

²Every 4 weeks through Week 24, then every 8 weeks through 52 weeks, then every 12 weeks.

³All sites of known disease must be assessed. To occur every 8 weeks during the first 52 weeks, then every 12 weeks.

⁴Patients with both bone and visceral metastases.

⁵Patients with bone metastases only. This is the **only tumor assessment for patients with bone metastases only**.

⁶ No additional measurements of plasma metanephrines are needed in patients with normal plasma metanephrines at baseline (Non-functioning PH or PG).

⁷ Starting after week 24, nursing phone calls to take place every 8 weeks, at the 4 week period between visits (+/- 5 days). After week 52, phone calls to take place every 12 weeks, at the 6 week period between visits (+/- 5 days). Phone calls will comprise AE and concomitant medication assessments.

⁸ MDASI questionnaires will be completed if the patient can be contacted and is willing and able to complete the questionnaire. While patients are encouraged to complete questionnaires at all scheduled time points, patients may refuse to complete a questionnaire at any time.

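### The only pre-dose blood markers and the bone-only FDG-PET may be taken while a patient is still on prior therapy; the markers can move to the existing visit within 4 days of dosing

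*Combined protocol and SAP*

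**What the plan says.** Table 5-1 (Section 5.2) has two pre-dose columns, headed "Within 28 days before 1st Dose of Study Treatment" and "Within 4 days before the first dose of Study Treatment". The rows "Plasma Metanephrines and Chromogranin A" and "Interleukin-6 and c- reactive protein, CTx" are marked in the first column and not in the second. The FDG-PET row for bone-only patients follows the same pattern. Footnote 3 then schedules all three rows every 8 weeks, so there is no other pre-dose sample or scan. Footnote 5 makes FDG-PET the sole tumor assessment in the bone-only branch. Vital signs, clinical laboratory tests and the symptom inventory (MDASI) are marked in both pre-dose columns.

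The washouts are in Section 4.2. Exclusion 5 reads "Receipt of any type of small molecule kinase inhibitor (including investigational kinase inhibitor) within 14 days before the first dose of study treatment". Exclusion 1 bars cytotoxic chemotherapy and biologic agents "within 3 weeks, or nitrosoureas/ mitomycin C within 6 weeks before the first dose of study treatment". Both count back from the first dose, not from the baseline sample or scan.

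Footnote 6 of Table 5-1 adds: "No additional measurements of plasma metanephrines are needed in patients with normal plasma metanephrines at baseline". It describes these patients as having non-functioning tumors.

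In Section 2.1, these measures feed secondary endpoint 4 (metanephrines and chromogranin A against tumor response), secondary endpoint 5 (CRP and IL-6 against symptoms and response), and exploratory endpoints 1 and 2 (FDG-PET response and uptake measures) and 5 (bone turnover, including CTx).

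**The concern.** The sampling window is longer than the washouts, and nothing ties one to the other. A patient can have blood drawn and a PET scan on Day -28, keep taking a kinase inhibitor until Day -15, and start cabozantinib without a protocol deviation. If the earlier drug had lowered a marker or FDG uptake, a later fall under cabozantinib would look smaller than it is, or a return to the off-drug level would look like a rise. Only recently pretreated patients would be affected, so the error would not be spread evenly across the sample.

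Such patients are foreseeable. The Hypothesis text in Section 1.1 motivates the trial by resistance to sunitinib.

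Two features make the baseline value matter more than usual. Under footnote 6, one normal metanephrine result is enough to stop that series. Also, for secondary endpoint 5 the symptom score can have an off-drug baseline from the 4-day visit while IL-6 and CRP in the same patient have an on-drug one.

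**Working it through.** **1. Permitted overlap.** Inputs: a sampling window of Day -28 to Day -1, which is 28 days (Table 5-1), and washout length w in days before first dose (Section 4.2). Days on which a compliant baseline can coincide with prior therapy = max(0, 28 - w).

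- Kinase inhibitor, w = 14: 28 - 14 = 14 days (Day -28 to -15); 14/28 = 50% of permitted days.
- Most chemotherapy and biologics, w = 21: 28 - 21 = 7 days (Day -28 to -22); 7/28 = 25%.
- Nitrosoureas and mitomycin C, w = 42: none.
- Other investigational agents, w = 28: none.

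These counts move by a day depending on how the boundary day is treated. They are shares of permitted days, not of patients.

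**2. Does another provision close the gap?**

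- Section 5.1 rechecks eligibility at screening and on Day 1. This does not help, because the washouts are measured from first dose.
- Section 3.4.4 prohibits other systemic anticancer treatment during the study. This helps in part, but the document does not define when being on study begins. Section 5.1 also lets routine-care tests done before consent count as screening.
- No section defines baseline as an off-drug value or calls for a repeat.

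**3. How large could the distortion be?** The documents give no suppression figure for the five markers under prior therapy, so b below is an assumption. Let b be the fraction by which prior drug lowers the baseline, and suppose cabozantinib truly lowers the measure by 30% from its off-drug level. Recorded change = 0.70/(1 - b) - 1.

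| b | Recorded change |
|---|---|
| 0 | -30% |
| 0.10 | 0.70/0.90 - 1 = -22% |
| 0.20 | 0.70/0.80 - 1 = -12.5% |
| 0.30 | 0.70/0.70 - 1 = 0% |
| 0.40 | 0.70/0.60 - 1 = +17% |
| 0.50 | 0.70/0.50 - 1 = +40% |

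The one related figure for a prior-type drug is in Section 1.1: tumors that responded to sunitinib "also exhibited more than 30% reduction in glucose uptake 2-3 months after initiation of treatment compared with baseline". It concerns FDG uptake, and responders only.

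**4. The bone-only branch.** The plan's interval reproduces as 0.45 ± 1.96 × √(0.45 × 0.55/8) = 0.45 ± 0.345, or 10.5% to 79.5%. One patient classified differently moves the rate by 1/8 = 12.5 points. The gap does not change this interval's arithmetic.

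**5. After moving the blood draw.** A sample within 4 days of dosing lies inside both the 14-day and the 21-day washout, so the permitted overlap for the five markers falls from 14 or 7 days to 0.

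**The case against.** The case for leaving the schedule alone has several sound parts.

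- **The exposure data already exist.** Section 3.4.2 records all medications from 28 days before first dose, exactly the window in question, and Table 5-1 collects cancer history. On-drug baselines can be identified afterwards. This stands and settles the PET part of the remedy. It does not recover an off-drug marker value that was never drawn.
- **Change from baseline is not specified.** A reader might infer that every biomarker correlation uses change from this baseline. Section 2.1 says only that the markers will be correlated, exploratory endpoints 2 and 5 are simply listed measures, and Section 7 says longitudinal models may be explored. The effect is conditional on the analysis chosen.
- **The 30% figure does not carry over.** A reader might take it as the expected suppression of any marker. Besides being limited to responders and FDG uptake, it sits uneasily with inclusion 5, which requires progression within 12 months. Patients progressing on a prior drug may show less suppression.
- **Footnote 6 might be said to drop true secretors.** No section shows prior therapy bringing a secretor's metanephrines to normal. The footnote is also permissive, and Section 5.2 allows more frequent assessments if clinically indicated. What remains is that one possibly on-drug result may decide the matter.
- **A later sample is not perfect.** At the 4-day visit, the last kinase-inhibitor dose could be only about 10 days earlier (14 - 4), so rebound could be captured. That is a fair limit, but the value would at least be off drug and close to dosing.

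**Conclusion.** The gap is real and modest. A compliant baseline for the five markers and the bone-only PET can be an on-prior-drug value on 14 of 28 permitted days (kinase inhibitor) or 7 of 28 (most chemotherapy and biologics), and the ban in Section 3.4.4 is only a partial safeguard. The number of patients affected and the direction of any bias are unknown: suppression would hide a later fall, and rebound after stopping could resemble progression. The table of recorded changes shows sensitivity under assumed suppression and is not a forecast.

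The point reaches secondary endpoints 4 and 5 and exploratory endpoints 1, 2 and 5, only so far as they are analysed relative to baseline, plus the footnote 6 decision. Two wider readings should be resisted. Because Section 1.1 says sunitinib improved blood pressure, a reader might extend the concern to blood pressure or MDASI; both have a reading within 4 days of dosing. A reader might also conclude that the primary result is undermined. CT and MRI share the 28-day window, but the documents give no figure for the effect on lesion size, and the stated interval for 14 patients is unchanged. This is a cheap improvement to secondary and exploratory measures, worth making because a missed baseline cannot be recovered after dosing.

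**What to change.** **Blood markers.** In Table 5-1, move the pre-dose mark for metanephrines, chromogranin A, IL-6, CRP and CTx to the existing visit within 4 days of first dose. State that this sample is the baseline, and apply footnote 6 to it. Align footnote 1, which places CTx at screening.

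**FDG-PET.** Do not add a drug-free interval before the scan; that could delay dosing and is not needed. Use the medication record in Section 3.4.2 with the cancer history to flag baseline scans taken on prior therapy, and report PET change with and without them. This assumes that stop dates are captured.

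**Cost.** One schedule amendment, resting-sample logistics for metanephrines at a visit where blood is already drawn, and one short sensitivity analysis. Because the draw is moved and not added, there are no extra assays. Washouts, sample size and the stated intervals stay as they are.

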5.3 Post-Treatment Period

Subjects will return to the study site 30 to 37 days after their last dose of cabozantinib to complete end-of-study assessments.

Laboratory and physical examinations will be performed. Remaining study treatment will be returned by the subject, and treatment compliance will be documented. Additional follow-up will occur for subjects with AEs related to study treatment that are ongoing at the time of this visit, and for subjects with SAEs related to study treatment that occur after the time of this visit.

²Every 4 weeks through Week 24, then every 8 weeks through 52 weeks, then every 12 weeks.

³All sites of known disease must be assessed. To occur every 8 weeks during the first 52 weeks, then every 12 weeks.

⁴Patients with both bone and visceral metastases.

⁵Patients with bone metastases only. This is the **only tumor assessment for patients with bone metastases only**.

⁶ No additional measurements of plasma metanephrines are needed in patients with normal plasma metanephrines at baseline (Non-functioning PH or PG).

⁷ Starting after week 24, nursing phone calls to take place every 8 weeks, at the 4 week period between visits (+/- 5 days). After week 52, phone calls to take place every 12 weeks, at the 6 week period between visits (+/- 5 days). Phone calls will comprise AE and concomitant medication assessments.

⁸ MDASI questionnaires will be completed if the patient can be contacted and is willing and able to complete the questionnaire. While patients are encouraged to complete questionnaires at all scheduled time points, patients may refuse to complete a questionnaire at any time.

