2.2 Study Design

2.2.1 Overview of Study Design

This is a single-arm, open-label phase II study of cabozantinib in subjects with malignant pheochromocytomas and paragangliomas. The primary endpoint is to estimate best overall response rate by RECIST 1.113 in patients with measurable disease determined by a. CT or b. MRI.

The primary objective is to estimate the best overall response rate in patients with measurable disease. Response will include RECIST 1.1 CR, PR, and SD. With 14 patients, the 95% confidence interval for a 45% response rate would be (18.9, 71.1%). For the exploratory objective in the small group of patients with bone metastases, the 95% confidence interval for a 45% response rate with 8 patients would be (10.5, 79.5%). We do not include a formal statistical monitoring rule for toxicity given the established safety profile of this drug.

Continuous variables will be summarized using descriptive statistics such as mean, standard deviation, median and range. Categorical variables will be tabulated by frequencies and the corresponding percentages. Response rates and their 95% confidence intervals will be estimated. Kaplan Meier survival curves will be used to estimate survival outcomes. Cox proportional hazards regression analysis may be used to assess the association between survival and covariates of interest. The Fisher's exact test or logistic regression analysis will be used for any binary outcomes. T-tests or Wilcoxon rank sum tests will be used to compare continuous variables. Longitudinal models may be explored to study change over time.

Each subject's course will consist of three periods:

- A Pre-Treatment Period in which subjects are consented and undergo screening assessments to be qualified for the study (Section 5.1);
- A Treatment Period in which subjects receive study treatment and undergo study assessments (Section 5.2);

• A Post-Treatment Period in which subjects no longer receive study treatment but undergo follow-up study assessments and contacts (Section 5.3).

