6 SAFETY

6.1 Adverse Events and Laboratory Abnormalities

6.1.1 Adverse Events

An AE is any untoward medical occurrence in a patient or clinical investigation subject who has been enrolled in a clinical study and who may have been given an investigational product, regardless of whether or not the event is assessed as related to the study treatment. An AE can therefore be any unfavorable and unintended sign (including an abnormal laboratory finding), symptom, or disease temporally associated with the use of an investigational product, regardless of whether or not the event is assessed as related to the investigational product. Pre-existing medical conditions that worsen during a study should be recorded as AEs. Abnormal laboratory values, ECG findings, or vital signs are to be recorded as AEs if they meet the criteria described in Section 3.3.

All untoward events that occur after start of study drug through 30 after the decision to discontinue study treatment (or the date the subject is deemed to be a screen failure) are to be recorded by the investigational site. This requirement includes AEs from unscheduled as well as scheduled visits.

Adverse events will be documented in the patient's official medical record and in the patient's essential source document. All grades will be recorded in the electronic database (CORe), and the attribution of Not-Related and Related will be assessed. Assessment of the relationship of the AR to the study treatment by the investigator is based on the following two definitions:

- Not Related: A not-related AE is defined as an AE that is not associated with the study treatment and is attributable to another cause or there is no evidence to support a causal relationship;
- Related: A related AE is defined as an AE where a causal relationship between the event and the study treatment is a reasonable possibility. A reasonable causal relationship is meant to convey that there are facts (eg, evidence such as dechallenge/rechallenge) or other clinical arguments to suggest a causal relationship between the AE and study treatment.

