- All life-threatening or fatal events, that are unexpected, and related to the study drug, must have a written report submitted within 24 hours (next working day) of knowledge of the event to the Safety Project Manager in the IND Office.
- Unless otherwise noted, the electronic SAE application (eSAE) will be utilized for safety reporting to the IND Office and MDACC IRB.
- Serious adverse events will be captured from the time of the first protocol-specific intervention, until 30 days after the last dose of drug, unless the participant withdraws consent. Serious adverse events must be followed until clinical recovery is complete and laboratory tests have returned to baseline, progression of the event has stabilized, or there has been acceptable resolution of the event.

Additionally, any serious adverse events that occur after the 30 day time period that are related to the study treatment must be reported to the IND Office. This may include the development of a secondary malignancy.

Reporting to FDA:

 Serious adverse events will be forwarded to FDA by the IND Sponsor (Safety Project Manager IND Office) according to 21 CFR 312.32.

It is the responsibility of the PI and the research team to ensure serious adverse events are reported according to the Code of Federal Regulations, Good Clinical Practices, the protocol guidelines, the sponsor's guidelines, and Institutional Review Board policy.

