6.2.4 Follow-Up of Adverse Events

Any related SAEs or any AEs assessed as related that led to treatment discontinuation, including clinically significant abnormal laboratory values that meet these criteria, ongoing 30 days after the decision to discontinue study treatment must be followed until either resolution of the event or determination by the investigator that the event has become stable or irreversible. This follow-up guidance also applies to related SAEs that occur > 30 days after the decision to discontinue study treatment. The status of all other continuing AEs will be documented as of 30 days after the decision to discontinue study treatment.

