12.3 Case Report Forms

For enrolled subjects, all and only data from the procedures and assessments specified in this protocol and required by the CRFs should be entered on the appropriate CRF. PDMS and CORe will be used as the eCRFs for this trial. Data from some procedures required by the protocol, such as physical examinations and laboratory results, will be recorded only on the source documents and will not be transcribed to eCRFs. Additional procedures and assessments may be performed as part of the investigator's institution or medical practice standard of care and may not be required for eCRF entry.

For each subject enrolled, the eCRF must be completed by an authorized delegate from the study staff.

The investigator should ensure the accuracy, completeness, legibility, and timeliness of the data in the eCRFs and in all required reports.

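### Bone-only branch (n=8): bone-specific alkaline phosphatase is an endpoint with no scheduled test, and no collection of disease-related skeletal events is planned after the visit 30–37 days post last dose, although incidence is to be reported at one year

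*Combined protocol and SAP*

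**What the plan says.** **Endpoints.** The synopsis and Section 2.1 list, for patients with bone metastases only, time to SRE, SRE incidence at 4 months and at one year, and two bone-turnover markers: bone-specific alkaline phosphatase and CTx. Section 1.1 describes SREs by example (bone pain, fracture, cord compression requiring radiation or surgery). No operational definition or SRE censoring rule is given.

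**Bone markers.** Table 5-1 has a CTx entry. Its footnote 1 sets CTx for patients with bone metastases at screening, 8-weekly to week 52, then 12-weekly. The chemistry panel in that footnote and in Section 5.4 includes alkaline phosphatase without specifying the bone isoform.

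**After treatment.** Table 5-1 has no SRE row, and its post-treatment column has one time point. Section 5.3 says: "Subjects will return to the study site 30 to 37 days after their last dose of cabozantinib to complete end-of-study assessments". Beyond that visit:

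- Section 5.3: "Additional follow-up will occur for subjects with AEs related to study treatment that are ongoing at the time of this visit", and likewise for treatment-related SAEs arising later.
- Section 6.1.1 sets the AE recording window: "All untoward events that occur after start of study drug through 30 after the decision to discontinue study treatment" (the unit, evidently days, is missing).
- Section 6.2.4, for everything other than the related events it lists: "The status of all other continuing AEs will be documented as of 30 days after the decision to discontinue study treatment".
- Section 6.1.2: "any serious adverse events that occur after the 30 day time period that are related to the study treatment must be reported". Section 6.1.3 extends late reporting to SAEs related to treatment or study procedures.

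Sections 2.5, 5.2 and 5.5 end treatment at progression unless continued benefit is judged case by case. Section 7 plans Kaplan-Meier curves for survival outcomes in general.

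**The concern.** The schedule, followed exactly, never produces one of the two named bone markers.

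For SREs, a fracture or cord compression caused by bone disease will not usually be attributed to the drug. Once the 30-day window closes, none of the later routes asks for it. A patient who stops before about month 11 and has had no SRE by then cannot be classified at one year.

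Those who leave observation will mostly be those who have progressed. If progression raises SRE risk, their censoring is informative and a Kaplan-Meier estimate at one year would be too low. A simple proportion that treated unknown status as no SRE would also be too low.

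**Working it through.** **1. The plan's own figure.** The only precision stated for this branch is for a 45% response rate with n=8: 0.45 ± 1.96 × √(0.45 × 0.55 / 8) = 0.45 ± 0.345, i.e. 10.5% to 79.5%. This reproduces. No precision is stated for the SRE or marker endpoints.

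**2. Bone-specific alkaline phosphatase.** No arithmetic is needed. The endpoint list names the marker; Table 5-1, its footnotes and Section 5.4 contain no such test. The panel's alkaline phosphatase cannot stand in for it, because Sections 1.1.1.5 and 1.1.1.6 themselves treat total and bone-specific alkaline phosphatase as different markers.

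**3. Who lacks planned SRE observation to one year.** Last planned contact is 30 to 37 days after last dose. Full observation to day 365 needs a last dose on or after day 365 − 37 = 328 to 365 − 30 = 335, about month 11. This step needs no model.

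**4. Illustrative size.** Inputs:

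- Median time to progression 11.2 months, from the cabozantinib arm of the medullary thyroid cancer trial (Section 1.1.1.5): a different tumour.
- Median time to SRE 4.4 months (Section 1.1, timed from development of bone metastases, not first dose), up to 20 months (assumed).
- Exponential times; treatment stops at progression; last contact L = 30/30.4375 = 0.986 or 37/30.4375 = 1.216 months later. Deaths and toxicity stops are ignored.

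With a = ln2/11.2 = 0.0619 and b = ln2/(SRE median), the probability of leaving observation before T without an SRE, under independence, is

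M(T) = e^(−bL) × a/(a+b) × [1 − e^(−(a+b)(T−L))].

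- SRE median 4.4, L = 37 days, T = 12: b = 0.1575; 0.826 × 0.282 × 0.906 = 0.211.
- SRE median 20, L = 30 days, T = 12: b = 0.0347; 0.966 × 0.641 × 0.655 = 0.406.

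So one-year status is missing for about 21–41%, or 1.7 to 3.2 of 8. About 4 of 8 leave observation before one year, since 1 − e^(−a(12−L)) is 0.49; the remainder of these already have an SRE on record. At T = 4 months the range is 11–16%.

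Sensitivity at one year:

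| Change (all assumed) | Missing status |
|---|---|
| Progression median 8 months | 27–51% |
| Progression median 15 months | 17–33% |
| Progression detected only at 8-weekly scans | 17–35% |
| 25% treated beyond progression | 16–30% |
| Progression and SRE times correlated 0.5 (Gaussian copula, 37-day visit) | 12–36% |
| Correlated 0.7 (same) | 7–34% |

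**5. Kaplan-Meier bias.** Let the SRE hazard be multiplied by k after progression (k assumed), with SRE medians 4.4, 10 and 20 months. True minus Kaplan-Meier 12-month incidence is 0 for k = 1, 2–4 points for k = 1.5, 3–6 points for k = 2 and 3–9 points for k = 3. The sampling half-width with 8 fully followed patients is 1.96 × √(q(1−q)/8). For q = 1 − 2^(−12/4.4) = 0.849 it is 25 points; for q = 1 − 2^(−12/20) = 0.340 it is 33 points.

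**The case against.** The best defence is that post-treatment contact is foreseen. Section 2.2.1 says that "subjects no longer receive study treatment but undergo follow-up study assessments and contacts", and Table 5-1 has a Follow-up row. But Section 2.2.1 refers to Section 5.3 for the detail, which schedules nothing for SREs, and the Follow-up tick sits in the same 30–37 day column.

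A reader might infer that late SREs are definitely not collected, citing Section 12.3: "all and only data from the procedures and assessments specified in this protocol and required by the CRFs should be entered". That goes too far. The sentence depends on what the CRFs require, and the CRFs are not in the documents. What can be said is that no collection is planned in the protocol.

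A reader might also take footnote 7 of Table 5-1, "Starting after week 24, nursing phone calls to take place every 8 weeks", as evidence of an early on-treatment gap. It is not: visits are every 2 to 4 weeks until week 24, with continuous AE recording. The calls are relevant only because they belong to the treatment period.

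Section 9.4, which says that samples are collected only for safety testing, is tempting as proof that the bone marker could not be measured later. It is weak evidence, since it equally conflicts with the scheduled CTx and interleukin-6, and the point does not need it.

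Observing SREs on treatment plus about 30 days is a defensible choice for 8 exploratory patients. That objection stands in part: the window could be kept, but it must then be stated, and an unqualified one-year incidence does not fit it. It is also fair that independence of progression and SRE times matters to the size; in bone-only disease the two may cluster, which lowers the missing fraction.

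**Conclusion.** Both parts hold, as a minor point on exploratory endpoints; the primary endpoint is not affected. The missing marker test is certain on the text. So is the absence of any written plan to collect disease-related SREs after the 30–37 day visit. Patients still on treatment at about month 11, including those treated beyond progression, remain observed, and an SRE judged treatment-related would still be reported.

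The size is only indicative: 21–41% with unknown one-year status under independence, 7–36% under assumed correlations of 0.5 to 0.7. Both rest on a progression median from another tumour and a partly assumed SRE median; toxicity stops would add to the missing status. The 4-month endpoint is less exposed. A reader might infer that the one-year estimate would be seriously biased. The documents do not support that: under the assumed hazard increases, the bias is well below the sampling error.

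**What to change.** **Marker.** Add bone-specific alkaline phosphatase to the CTx draw in Table 5-1 and Section 5.4 for patients with bone metastases, or delete it from the endpoints. Cost: one added assay at existing draws, or nothing.

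**SREs.** In Section 5.3, Table 5-1 and the CRF, add brief phone contacts every 8–12 weeks after last dose until 12 months from first dose for bone-branch patients. Record SRE type and date, start of new anticancer therapy, and death. State which events count as an SRE. Report SREs to 12 months regardless of treatment, and do not count unknown status as no SRE.

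Alternatively, if only SREs on treatment plus about 30 days are wanted, put that window in the endpoint wording and drop the unqualified one-year incidence.

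**Cost.** One protocol and CRF amendment with IRB approval (Section 10), and at most about 6 short calls per patient (52/8 = 6.5) for about 8 patients, with no extra scans or visits. SRE dates from calls rest on patient report unless outside records confirm them.
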